5 STATISTICAL METHODS

All descriptive statistics for continuous variables will be reported using n, mean, standard deviation (SD), median, 25th percentile (Q1), 75th percentile (Q3), minimum and maximum. Categorical variables will be summarized as number (percentage) of subjects. All data will focus on the following 4 parts. Part 1 will focus on Phase 1b including some Phase 2 data. Part 2-4 will specifically focus on the solid tumor cohorts for their safety and efficacy.

Phase 1b/2: Selected outputs (e.g., disposition, demographic and baseline and disease characteristics, study drug exposure, DLT, and adverse events) will be provided for phase 1b subjects. The overall summary of the corresponding Phase 2 data may be included for the presentation.

EC cohort: primarily the data will be summarized by MSI/MMR status (Non-MSI-H/pMMR, MSI-H/dMMR, Not Available) and for overall. Efficacy results will be summarized by PD-L1

status and by the number of previous anticancer regimens. The Phase 1b and Phase 2 data will be combined for the analyses. RCC cohort: Efficacy subgroup analyses may be presented by the number of previous anticancer regimens, by PD-L1 status, and by subjects who were previously treated with/without an anti-PD-1/PD-L1 therapy. The Phase 1b and Phase 2 data will be combined for the analyses, as appropriate.

Four other cohorts: each cohort will be summarized separately. The Phase 1b and Phase 2 data will be combined for the analyses, as appropriate.

5.1 Study Endpoints

5.1.1 Primary Endpoints

Primary Efficacy Endpoint for Phase 1b:

The primary objective of Phase 1b is to determine the DLTs, MTD, and to establish the RP2D.

Primary Efficacy Endpoint for Phase 2:

The primary objective of Phase 2 is to evaluate $ORR_{(Week\ 24)}$ in each of the cohorts using irRECIST. $ORR_{(Week\ 24)}$ is defined as the proportion of subjects who have the best overall response (BOR) of $CR_{(Week\ 24)}$ or $PR_{(Week\ 24)}$ as of the Week 24 tumor assessment time point. Subjects who did not have a tumor response assessment for any reason will be considered non-responders and will be included in the denominator when calculating the response rate.

5.1.2 Secondary Endpoint(s)

The secondary efficacy endpoints will be ORR, PFS, OS, DCR, CBR, DOR and durable SD by irRECIST ([Appendix 13.1](#)) as appropriate. The secondary efficacy endpoints are defined as follows.

- **ORR** is defined as the proportion of subjects who have BOR of partial or complete response (PR + CR) at the time of data cut-off. Subjects who do not have a tumor response assessment for any reason will be considered non-responders and will be included in the denominator when calculating the response rate.
- **PFS** is defined as the time from the first dose date to the date of the first documentation of disease progression or death (whichever occurs first) using irRECIST, see [Appendix 13.1](#). If a subject did not experience a disease progression or death, then the subject will be censored at the date of the last available tumor assessment.

- **OS** is measured from the start date of the treatment period until date of death from any cause. Subjects who are lost to follow-up and the subjects who are alive at the date of data cutoff will be censored at the date the subject was last known alive.
- **DCR** is defined as the proportion of subjects who have BOR of CR or PR or SD (minimum duration from C1D1 to SD ≥ 5 weeks).
- **CBR** is defined as the proportion of subjects who have BOR of CR or PR or durable SD (duration of SD ≥ 23 weeks).
- **DOR** is defined as the time from the date of the first documentation of the confirmed CR or PR (whichever occurs first) to the date of the disease progression objectively documented or death (whichever occurs first). If a subject had no record of disease progression or did not die before the data cut-off date, then the subject will be censored at the last available tumor assessment.
- **Durable SD rate** is defined as the proportion of subjects whose BOR is SD and the duration of SD is ≥ 23 weeks.

The safety endpoints include treatment-emergent adverse events (TEAEs), clinical laboratory parameters, vital signs, 12-lead ECGs, and echocardiogram/MUGA results including LVEF.

Determination of the plasma PK profile of lenvatinib while subjects are receiving combination therapy is also a secondary endpoint.

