9.7.1.1.2 SECONDARY ENDPOINTS (BOTH PHASE 1B AND PHASE 2)

The secondary efficacy endpoints will be ORR, PFS, OS, DCR, CBR, DOR, and durable SD rate (SD ≥ 23 weeks) by irRECIST as appropriate. The secondary efficacy endpoints are defined as follows.

- **ORR** is defined as the proportion of subjects who have BOR of irCR or irPR at the time of data cutoff.
- **PFS** is defined as the time from the first study dose date to the date of first documentation of confirmed disease progression or death (whichever occurs first). If a subject has not experienced disease progression or death, then the subject's data will be censored at the date of the last available tumor assessment.
- **OS** is measured from the start date of the treatment period until date of death from any cause. Subjects who are lost to follow-up and the subjects who are alive at the date of data cutoff will be censored at the date the subject was last known alive.
- **DCR** is defined as the proportion of subjects who have BOR of irCR or irPR or irSD (duration of irSD ≥ 5 weeks).
- **CBR** is defined as the proportion of subjects who have BOR of irCR or irPR or durable irSD (duration of irSD ≥ 23 weeks).
- **DOR** is defined as the time from the date the criteria are met for an irCR or irPR (whichever is recorded first) to the date the disease progression is objectively

documented. If a subject has no record of disease progression, then the subject's data will be censored at the last available tumor assessment.

- **Durable SD rate** is defined as the proportion of subjects whose BOR is irSD and the duration of irSD is ≥ 23 weeks.

Determination of the plasma PK profile of lenvatinib while subjects are receiving combination therapy also is a secondary endpoint.

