5.4 Efficacy Analyses

Tumor response will be assessed by both immune-related RECIST (irRECIST) and modified version of RECIST 1.1 criteria (mRECIST 1.1) per investigator assessment, and by irRECIST, mRECIST 1.1 and RECIST 1.1 per independent imaging review. All efficacy analyses will be performed on the Full Analysis Set for the specific cohort analysis set for EC, RCC and other cohorts. Tabular summary of key features of the efficacy analyses is described in [Appendix 12.5](#) (Summary of Efficacy Analyses). Tumor assessments and overall response to the treatment according to irRECIST are presented in [Appendix 13.1](#).

The best overall response (BOR) is determined once all the data for the subject is known. For this study, a confirmation of complete responses or partial responses is required for both irRECIST and modified RECIST 1.1; and following irRECIST, a confirmation of progression due to a tumor burden is required unless it is per investigator's discretion if the subject was

clinically unstable. The confirmation assessments should be made ≥ 4 weeks later. The BOR is determined by sequentially checking two adjacent assessments with ≥ 4 weeks apart (and with a few special cases). As an example if a subject had a stable disease at the timepoint 1, a partial response at the timepoint 2, a complete response at the timepoint 3, and another complete response at the timepoint 4, then the BOR for this subject is complete response, which was confirmed at the timepoint 4.

To program the BOR per irRECIST: (1) the tumor response data collected via both irRECIST and mRECIST 1.1 CRFs will be used; (2) any further response assessments after the second PD (confirmed PD per irRECIST) identified under irRECIST should not be considered for the BOR determination, however they should be presented in the data listings; (3) all tumor assessments as long as the subjects did not start a new anti-cancer therapy should be considered; (4) if there are more than 1 consecutive missing tumor assessments, all assessments afterward should not be considered for the determination of BOR (also see [Section 5.4.3](#) for PFS). The BOR per irRECIST is defined as follows. [Table 4](#) lists general rules in the derivation of BOR with two consecutive tumor response results (with a few special cases, see Table 4).

- **CR**

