To achieve BOR of CR, CR must be observed at two consecutive tumor assessment visits with at least 4 weeks apart before a PD or death (whichever occurs first). If complete responses at two consecutive tumor assessment visits were with less than 4 weeks, the confirmation of CR at the next assessment visit is required.

The documented start date of CR as the BOR is defined as the date of the initial CR that was confirmed at the next consecutive visit (≥ 4 weeks after the initial CR response).

- **PR**

When BOR of CR is not achieved, BOR of PR can be achieved when the initial PR was confirmed by a PR or CR at the next consecutive visit (≥ 4 weeks after the initial PR response). If the two PRs (or PR and then CR) happened at two consecutive tumor assessment visits within 4 weeks, the additional confirmation of the PR is needed.

The documented start date of PR as the BOR is defined as the date of the initial PR that was confirmed at the next consecutive visit (≥ 4 weeks after the initial PR response).

- **PD**

Following irRECIST, subject may continue treatment at the investigator's discretion after the initial PD due to pseudo-progression, if the subject is clinically stable. If a repeating imaging assessment at ≥ 4 weeks after the initial PD was not done, this initial PD response will be considered as a real PD. However, if there was subsequent tumor assessment (≥ 4 weeks) that showed a CR, PR or SD, regularly scheduled imaging assessments should be continued. The BOR will be determined based on all tumor assessments. When a PD is identified and confirmed under irRECIST, any further response assessments after the first PD under irRECIST should not be considered to determine BOR and PFS (i.e. the assessments up to the first PD under irRECIST will be considered for BOR and PFS), however these further assessments should be presented in the data listings.

The documented start date of PD is defined as the date of the initial PD that was confirmed at the next consecutive visit (i.e. a consecutive PD was identified ≥ 4 weeks after the initial PD response), or the date of the initial PD if a repeating imaging assessment was not done, or the date of the first PD identified during irRECIST evaluations.

- **UNK (Unknown)**

If the subject did not have a baseline tumor assessment, then BOR = UNK (Unknown).

- **NE (Not Evaluable)**

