5.4.1 Primary Analysis for Phase 1b

The primary objective of Phase 1b is to determine the DLTs, MTD, and to establish the RP2D. The endpoint DLTs in Phase 1b will be summarized based on the MTD Analysis Set.

5.4.2 Primary Efficacy Analysis for Phase 2

The primary efficacy endpoint in Phase 2 is objective response rate as of Week 24 (ORR_(Week 24)) based on irRECIST. The primary efficacy analysis of ORR(Week 24) for each cohort may be performed based on the Full Analysis Set when all subjects in that cohort have completed 8 cycles of treatment, or discontinued early due to disease progression, unacceptable toxicity, consent withdrawn, or the study termination by the Sponsor. Estimated ORR_(Week 24) and the exact 95% confidence intervals using the method of Clopper–Pearson will be presented.

5.4.3 Secondary Efficacy Analyses for Both Phase 1b and Phase 2

The following secondary efficacy analyses will be performed.

Objective Response Rate (ORR): The ORR is the proportion of patients achieving a best overall response of confirmed PR or CR at the time of data cutoff. Subjects who do not have a tumor response assessment for any reason will be considered non-responders and will be included in the denominator when calculating the response rate. The count and percentage for the ORR will be summarized. ORR and corresponding 95% CI based on exact binomial distribution will be estimated for each treatment cohort.

Progression-Free Survival (PFS): The PFS is defined as the time from the first study dose date to the date of first documentation of confirmed PD using irRECIST or death (whichever occurs first). If a subject has not experienced disease progression or death, then the subject's

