data will be censored at the date of the last adequate radiologic assessment. The PFS censoring rules in this SAP and definition of progression date follow the principles of the Food and Drug Administration (FDA) “[Guidance for Industry Clinical Trial Endpoints for the Approval of Cancer Drugs and Biologics \(2007\)](#)”. Due to the use of pembrolizumab, all tumor assessments up to the first PD identified under irRCIST are considered as long as the subjects did not start a new anti-cancer therapy. The date of radiological assessment is based on the date of scans performed for a time point. The date will be based on the time point required CT/MRI scans unless there is a new lesion on the bone scan(s) or brain scan(s) performed to ensure CR or PR, or on brain scan(s) performed to ensure CR. Table 5 shows the censoring rules for the derivation of PFS.

Table 5 Censoring rules for the derivation of PFS.

No.	Situation	Date of Event (Progression/Death) or Censoring	Outcome
1	No baseline tumor assessments	Date of first dose	Censored
2	Progression documented between scheduled visits	Date of first radiologic PD assessment	Event
3	No progression	Date of last adequate radiologic assessment	Censored
4	New anticancer treatment started	Date of last adequate radiologic assessment prior to or on date of new anticancer treatment	Censored
5	Death before first PD assessment	Date of death	Event
6	Death between adequate assessment visits*	Date of death	Event
7	Death or progression after more than one missed visit/tumor assessment**	Date of last adequate radiologic assessment before missed tumor assessments	Censored

CR = complete response, PD = progressive disease, PR = partial response, SD =stable disease,

* Adequate tumor assessment is radiologic assessment at regular interval as defined in the protocol.

** More than one missed visit/adequate tumor assessment is defined as having the duration between the last adequate tumor assessment and death or PD being longer than 14 weeks - 1 day, which is 97 days ($= ((6+1) \times 2 \times 7) - 1$) for subjects on the every 6 week tumor assessment schedule in the first 8 cycles of treatment and 20 weeks - 1 day, which is 139 days ($= ((9+1) \times 2 \times 7) - 1$) for subjects on the every 9 week tumor assessment schedule after Cycle 8 in this study.

The priority of the censoring rules is as follows,

1. If the subject had PD or death, the following sequence will be applied:

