Subject lost to follow-up before data cut-off	Date last known to be alive	Censored

Disease Control Rate (DCR): The DCR is the proportion of subjects who have BOR of CR or PR or SD (minimum duration from C1D1 to SD ≥ 5 weeks). The count and percentage with exact 95% CI for the DCR will be summarized.

Clinical Benefit Rate (CBR): The CBR is the proportion of subjects who have BOR of CR or PR or durable SD (duration of SD ≥ 23 weeks). The count and percentage with exact 95% CI for the CBR will be summarized.

Duration of Response (DOR): The DOR is defined as the time from the date of the first documentation of the confirmed CR or PR (whichever occurs first) to the date of the disease progression objectively documented or death (whichever occurs first). If a subject had no record of disease progression or did not die before the data cut-off date, then the subject will be censored at the last available tumor assessment. The distribution of DOR will be estimated using Kaplan–Meier Method. Median duration of response and 95% CI will be provided.

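### The SAP words the irRECIST PFS event both with and without confirmed progression, and its DOR censoring sentence, read literally, contradicts the DOR event

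*SAP*

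**What the plan says.** **PFS by irRECIST.** SAP 5.1.2 says that PFS "is defined as the time from the first dose date to the date of the first documentation of disease progression or death", using irRECIST as set out in Appendix 13.1. The word *confirmed* is absent. SAP 5.4.3 ends PFS at the "date of first documentation of confirmed PD using irRECIST or death", and Protocol 9.7.1.1.2 also requires confirmed progression.

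SAP 5.4 supplies the supporting rules. Under irRECIST "a confirmation of progression due to a tumor burden is required", with an exception for clinically unstable subjects. An initial PD with no repeat scan counts as real. If a later scan shows CR, PR or SD, assessment goes on and BOR uses all the scans. A confirmed PD is dated at the initial scan. The list of PD dates then closes with an alternative that carries no condition: "or the date of the first PD identified during irRECIST evaluations". SAP 5.4.3 adds that "all tumor assessments up to the first PD identified under irRCIST are considered". SAP Appendix 13.1, to which 5.1.2 points, only recommends confirmation.

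**DOR.** SAP 5.1.2 and 5.4.3 run from first documentation of the confirmed response to the earlier of progression and death. The next sentence, identical in both places, reads: "If a subject had no record of disease progression or did not die before the data cut-off date, then the subject will be censored". The censoring date it gives is that of the latest scan on file. Protocol 9.7.1.1.2 censors DOR only where there is no progression and does not name death as an event. SAP Section 7 declares no changes to the planned analyses.

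**The concern.** PFS and DOR are named secondary endpoints in every cohort, and these sentences are their event and censoring rules. SAP Section 9 leaves the derivations to separate programming documents, so the SAP has to fix the rule.

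For PFS, irRECIST differs from the modified RECIST 1.1 analysis because an early PD that later reverses is not counted as progression. A definition that takes the first documented PD loses that difference. It also allows an incoherent record, in which a subject has a PFS event and then a response that counts for BOR and starts the DOR clock.

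For DOR, the censoring sentence undoes the event definition that it follows. Since it appears in both sections, neither corrects the other.

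**Working it through.** The plan states no figure that depends on these sentences, so there is none to reproduce. The check compares the wording and then illustrates direction under assumed rates.

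**1. PFS: status of an initial PD under each text**

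| What follows the initial PD | SAP 5.1.2, or last clause of the 5.4 PD rule | SAP 5.4.3 opening, read with the rest of 5.4 |
|---|---|---|
| PD at least 4 weeks later | Event at initial PD | Event at initial PD |
| No repeat scan | Event at initial PD | Event at initial PD (counted as real) |
| NE | Event at initial PD | PD by Table 4 |
| CR, PR or SD at least 4 weeks later | Event at initial PD | Not an event; follow-up continues |

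The disagreement lies mainly in the last row.

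**2. One subject (hypothetical).** SD at Week 6, PD at Week 12, PR at Weeks 18 and 24, then a PD at Week 51 that is later confirmed. PFS is 12 weeks under the first column and 51 weeks under the second. BOR is PR either way, starting at Week 18. Under the first column, the response begins 6 weeks after the PFS event.

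**3. Effect on the PFS median.** Assumptions, none from the documents: exponential PFS with a 7-month median when confirmation is required, and a share q of subjects, independent of prognosis, with a reversed first PD at Week 6 (about 1.4 months). After 1.4 months the first-PD curve is S(t) = (1 − q) × 2^(−t/7), so the median is 7 × [1 + log2(1 − q)].

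- q = 0: 7.0 months
- q = 3%: 7 × (1 − 0.044) = 6.7 months
- q = 5%: 7 × (1 − 0.074) = 6.5 months
- q = 10%: 7 × (1 − 0.152) = 5.9 months

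A simulation of 200,000 subjects gave 6.7, 6.5 and 6.0 months for the last three.

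**4. DOR: truth table**

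| Progressed | Died by cutoff | Event sentence | Censoring sentence, literal |
|---|---|---|---|
| No | No | Censored | Censored |
| No | Yes | Event | Censored |
| Yes | No | Event | Censored |
| Yes | Yes | Event | Event |

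Two of the three event patterns are lost. Replacing the *or* by *and* makes the two columns agree in all four rows.

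**5. DOR: direction and size.** Simulation of 200,000 responders. Assumptions, none from the documents: exponential time to PD (median 9, 12 or 18 months) and survival after PD (median 6, 12 or 24 months), rare death without PD (median 120 months), and cutoff uniform at 12 to 30 months after response. Under the literal rule, a living progressor is censored at the PD scan.

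| Median to PD | Median survival after PD | Events: intended / literal | KM median: intended / literal |
|---|---|---|---|
| 9 | 6 | 0.81 / 0.55 | 8.3 / 11.5 |
| 9 | 12 | 0.81 / 0.39 | 8.4 / 19.6 |
| 9 | 24 | 0.81 / 0.24 | 8.4 / not reached |
| 12 | 6 | 0.72 / 0.46 | 10.9 / 17.1 |
| 12 | 12 | 0.72 / 0.33 | 10.9 / not reached |
| 12 | 24 | 0.72 / 0.20 | 10.9 / not reached |
| 18 | 6 | 0.60 / 0.35 | 15.7 / not reached |
| 18 | 12 | 0.59 / 0.25 | 15.7 / not reached |
| 18 | 24 | 0.60 / 0.15 | 15.6 / not reached |

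The intended medians agree with the closed form m × 120/(m + 120): 8.4, 10.9 and 15.7 for m = 9, 12 and 18. The share of events kept runs from 0.15/0.60 = 25% to 0.55/0.81 = 68%. The bias is upward in every row.

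**The case against.** The strongest reply is that the intent can be recovered. SAP 5.1.2 ties PFS to irRECIST, SAP 5.4 requires confirmation under irRECIST, and SAP 5.4.4 treats pseudoprogression as PD only under modified RECIST 1.1 and RECIST 1.1. Programming the opening sentence of 5.4.3 gives the protocol's PFS. For DOR, the event sentence stands immediately before the faulty one, and the PFS censoring sentence in 5.1.2 shows the construction that was meant. Both endpoints are secondary and are estimated without statistical comparison.

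Most of this stands, and it rules out three stronger readings that a reader might infer.

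- *Most of the SAP's sentences make an unconfirmed PD an event, so irRECIST PFS collapses to a first-PD PFS.* The documents do not support this. The scan cutoff in 5.4.3 echoes the PD rule in 5.4, where the cutoff at the first PD applies to a PD that has been identified and confirmed. It selects scans and does not by itself create an event. What remains is the missing word in 5.1.2, the unconditional last clause in 5.4, and the weaker verb in Appendix 13.1.
- *PFS will be wrong whichever sentence is programmed.* It will not, because 5.4.3 agrees with the protocol. The fault is inconsistent definition.
- *The DOR sentence removes most progressions.* That depends on the assumed rates. With median time to PD and median survival after PD both 12 months, about 39% of progressions are kept for a cutoff at 6 to 24 months and about 55% for 12 to 36 months. With 6-month survival after PD, the figures are about 59% and 75%.

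The reply does not remove the contradictions. An SAP should not depend on the programmer to infer which of two sentences to ignore.

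**Conclusion.** The point holds as a wording fault in operative rules for two secondary endpoints.

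The PFS event is inconsistently defined. The consequence is confined mainly to subjects whose first PD is followed by CR, PR or SD. Their share is not in the documents; the shift in the median from 7.0 to between 6.7 and 5.9 months rests wholly on the assumed 3% to 10% and on the other assumptions of step 3.

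The DOR censoring sentence contradicts the DOR event. That follows from the text alone, as does the upward direction of the bias if it is coded literally. The size does not: across the assumed rates it runs from a few months on the median to a median that is not reached.

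The primary ORR at Week 24, the numerical expansion boundaries and the sample size do not depend on these sentences. The change should be made, but the fault does not threaten the primary analysis.

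**What to change.** 1. SAP 5.1.2: add *confirmed* to the PFS progression event.
2. SAP 5.4, PD rule: delete the last alternative for the PD date, or make it conditional on confirmation.
3. SAP 5.4.3: keep the scan cutoff, and state that first PD means one of the following: the initial scan of a confirmed PD; an initial PD with no evaluable repeat scan (none done, or NE as in Table 4); or a PD under the clinically unstable exception in 5.4. A PD followed at least 4 weeks later by CR, PR or SD is then not an event.
4. SAP Appendix 13.1: align its statement on confirmation with the analysis rule in 5.4.
5. SAP 5.1.2 and 5.4.3, DOR: censor only when neither progression nor death has been recorded by the data cutoff, and use the same PD date as for PFS.
6. Reconcile death as a DOR event with Protocol 9.7.1.1.2. If the SAP keeps it, list it in SAP Section 7.

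The cost is SAP wording and one programming specification. No new data are needed.
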